## 1. Version History

Version	Summary of Changes	Author(s)/Title
1.0	
 
Not Applicable, New Document
 
	[name], Prin. Field Clinical Site Specialist [name], Prin. Statistician [name], Sr. Principal Scientist [name], Distinguished Field Clinical Engineer
2.0	
 
Refer to Appendix G Table 17 for detailed changes
 
	[name], Prin. Clinical Research Specialist [name], Sr. Principal Scientist
3.0	
 
Refer to Appendix G Table 18 for detailed changes
 
	[name], Prin Field Clinical Engineer [name], Prin Statistician [name], Sr Statistician [name], Sr Prin Scientist

## 2. Investigator Statement

Investigators will be provided with a separate investigator agreement to document their obligation and commitment with respect to study conduct.

### 3. Glossary

Term/Abbreviation	Definition
ACE	Angiotensin Converting Enzyme
ADE	Adverse Device Effect
ADL	Activities of Daily Living
AE	Adverse Event
ARB	Angiotensin Receptor Blocker
Bpm	Beats per minute
BNP	B-type Natriuretic Peptide
CIP	Clinical Investigation Plan
CH	Concentric Hypertrophy
CRF	Case Report Form
CTA	Clinical Trial Agreement
CV	Curriculum Vitae
Data protection authorization	A/an Authorization to Use and Disclose Personal Health Information/Research Authorization/other privacy language
DD	Device Deficiency
Echo	Echocardiography
eCRF	Electronic Case Report Form
ERI	Elective Replacement Indicator
Ethics Committee	MEC/IRB/HREB/Ethics Board
FAL	Foreseeable Adverse Event List
FDA	Food and Drug Administration
FDAAA	Food and Drug Administration Amendments Act

Term/Abbreviation	Definition
GCP	Good Clinical Practice
Hall Walk	6 Minute Walk Test
HF	Heart Failure
HFpEF	Heart Failure With Preserved Ejection Fraction
HFREF	Heart Failure With Reduced Ejection Fraction
IC Form	Informed Consent Form
IDE	Investigational Device Exemption
IRB	Institutional Review Board
LBBB	Left Bundle Branch Block
LV	Left Ventricular
LVEF	Left Ventricular Ejection Fraction
LVH	Left Ventricular Hypertrophy
MN	Minnesota
MNLWHF	Minnesota Living With Heart Failure
MMPs	Matrix Metalloproteinases
MRA	Mineralocorticoid Receptors Antagonist
MRI	Magnetic Resonance Imaging
NSR	Non-Significant Risk
NT-proBNP	N-terminal pro b-type Natriuretic Peptide
NYHA	New York Heart Association
OC	Oracle Clinical (electronic database)
QOL	Quality of Life
RA	Right Atrial

Term/Abbreviation	Definition
SADE	Serious Adverse Device Effect
SAE	Serious Adverse Event
SC	Steering Committee
SVT	Supraventricular Tachycardia
TIC	Tachycardia induced dilated cardiomyopathy
TIMPs	Tissue inhibitors of metalloproteinases
TriV	Tri-ventricular
UR	Upper Rate
UADE	Unanticipated Adverse Device Effect
USADE	Unanticipated Serious Adverse Device Effect
WO	Work Order

## 4. Synopsis

Title	REVAMP Clinical Study ( RE modeling the Left V entricle with A trial M odulated P acing)
Clinical Study Type	Feasibility
Product Name	Medtronic dual chamber pacemakers with a Sleep function including: Kappa 700, Kappa 900, Adapta, Versa, Sensia, EnPulse, Advisa, Advisa MRI, and additional Medtronic dual chamber pacemakers with the Sleep Function as they become market released
Sponsor/Local Sponsor	Medtronic, Inc. Cardiac Rhythm and Heart Failure Clinical Research [name] U.S.A. [name]
Indication under investigation	New therapy tested in heart failure with preserved ejection fraction (HFpEF) patients with approved indications for pacing
Investigation Purpose	The REVAMP Clinical Study is a feasibility study in heart failure with preserved ejection fraction (HFpEF) patients who have normal to small left ventricular volumes and evidence of hypertrophy. The pacemaker Sleep function will be used in order to deliver a 5 hour block of sustained pacing at 100 bpm during the night for 4-8 weeks. The purpose is to investigate whether this elevated pacing therapy is tolerated and whether there is a signal of efficacy.
Product Status	The study will be conducted using market-released Medtronic dual chamber pacemaker devices with a Sleep function and a Medtronic programmer. The protocol will specify the programming of the Sleep Rate and Pacing Parameters in order to deliver elevated atrial pacing rates during the time when the patient is sleeping.
Primary Objective(s)	The primary objective of this study is to assess the feasibility of using elevated night pacing as a therapy for heart failure with preserved ejection fraction.
Ancillary/Exploratory Objective(s)	Collect and characterize adverse events, quality of life, 6 Minute Walk Test, echo measurements and blood biomarker data at Baseline and follow-up visits
Study Design	The REVAMP Clinical Study will be a multi-center, prospective, randomized, single-blinded, clinical feasibility study.
Randomization	Subjects will be randomized at the 4 week follow-up visit to a 2:1 ratio to elevated night pacing ON or elevated night pacing OFF.

Sample Size	It is expected that up to 50 subjects may be enrolled to ensure 30 subjects undergo elevated night pacing at approximately 10 sites in the United States only.
Inclusion/Exclusion Criteria	
Inclusion criteria:
 
 
• Subject has had a market released dual chamber Medtronic Pacemaker with a Sleep function for at least 3 months
 
• Subject is stable on current medications
 
• Subject has dyspnea with exertion or diagnosed as NYHA Class II or III heart failure.
 
• Subject has had a prior Echo in past 6 months with: EF <math>\geq</math> 50% and Diastolic volume <math>\leq</math> 80 ml/m^2
 
• Subject has evidence of hypertrophy (indexed to body surface area: men 115 g/m^2, women 95 g/m^2 or indexed to height: men 49.2 g/m2.7, women 46.7 g/m2.7) or Relative Wall thickness <math>></math> 0.42, or Wall Thickness <math>\geq</math> 1.2cm (posterior wall)
 
• Subject is willing to sign and date the study Informed Consent Form
 
• Subject is 18 years of age or older, or of legal age to give informed consent per local law
 
• Subject is expected to remain available for follow-up visits
 
 
Exclusion criteria:
 
 
• Subject has permanent AF or AF noted on baseline interrogation rhythm strip
 
• Subject has uncontrolled BP; (systolic pressure needs to be <math>></math> 100mmHg and <math><</math> 160mmHg on medications)
 
• Subject has severe stenosis of the aortic or mitral valve, defined as a valve area <math>\leq</math> 1.0 cm^2 or subject has severe regurgitation of the aortic or mitral valve.
 
• Subject has symptomatic COPD requiring oxygen
 
• Subject's Pacemaker has less than 6 months of Pacemaker battery life
 
• Subject had an aortic valve replacement (surgical or TAVR) procedure less than 9 months prior to enrollment
 
• Subject's programmed upper rate limit is less than 100 bpm because of concerns of elevated pacing
 
• Subject is unable or unwilling to perform the 6 Minute Walk Test at all scheduled study visits
 
• Subject is currently enrolled or planning to enroll in a potentially confounding trial during the course of the study (co-enrollment in concurrent studies is only allowed when documented pre-approval is obtained from the Medtronic study manager)
 
• Subject is pregnant
 
• Subject meets any exclusion criteria required by local law
 

	
 
• Subject's life expectancy is less than 12 weeks
 
• Subject with a medical condition that precludes the patient from participation in the opinion of the investigator
 
• Subject has known coronary disease with Class II angina
 

Study Procedures and Assessments
	
In Office Visits: Study procedures, assessments and in-clinic data collection will be at Enrollment/Baseline, 4 weeks, 8 weeks and 12 week visits.
 
Telephone Call Follow Up Visits: Subjects will be called at regular intervals after their Baseline visit: 24 hours, 5 days, 2 weeks, 6 weeks, and 10 weeks to inquire about symptoms. Subjects will also be asked their heart rate which the subject can read using a finger pulse oximeter monitor that will be given to them at Baseline to use.
 
Enrollment Baseline:
 
 
• Informed Consent
 
• Verification of Inclusion/Exclusion criteria
 
• Subject Demographics
 
• Medical History
 
• Medications
 
• Physical Assessment (including height, weight, heart rate and blood pressure)
 
• NYHA classification
 
• MN Living with Heart Failure Questionnaire
 
• EQ-5D-5L Questionnaire
 
• 6 Minute Walk Test
 
• Blood Draw
 
• Echo
 
• Device Interrogation (initial)
 
• Save to media (initial)
 
• Program the sleep function to ON and program the pacing parameters
 
• Subject observation of at least 30 minutes to ensure the subject can tolerate 100 bpm pacing post programming
 
• Device Interrogation (final) - this needs to be completed at the end of the visit after programming has been completed
 
• Save-to-Media (final)
 
 
24 Hour Telephone Call Follow Up Visit:
 
 
• Symptom Assessment
 
• Heart Rate
 
 
5 Day Telephone Call Follow Up Visit:
 
 
• Symptom Assessment
 
• Heart Rate
 
 
2 Week Telephone Call Follow Up Visit:

	
 
• Symptom Assessment
 
• Heart Rate
 
 
4 Week In-Clinic Follow Up Visit (Randomization):
 
 
• Medications
 
• Physical Assessment (including weight, heart rate and blood pressure)
 
• NYHA classification
 
• MN Living with Heart Failure Questionnaire
 
• 6 Minute Walk Test
 
• Blood Draw
 
• Echo
 
• Device Interrogation (initial)
 
• Save-to-Media (initial)
 
• Program the sleep function to OFF if randomization assignment is OFF (and program the pacing parameters)
 
• Device Interrogation (final) - this needs to be completed at the end of the visit after programming has been completed
 
• Save-to-Media (final)
 
• Adverse Events (report new/assess ongoing AEs), Study Deviations, System Modifications, Device Deficiencies, Crossovers (as they occur)
 
 
6 Week Telephone Call Follow Up Visit:
 
 
• Symptom Assessment
 
• Heart Rate
 
 
8 Week In-Clinic Follow Up Visit:
 
 
• Medications
 
• Physical Assessment (including weight, heart rate and blood pressure)
 
• NYHA classification
 
• MN Living with Heart Failure Questionnaire
 
• EQ-5D-5L Questionnaire
 
• 6 Minute Walk Test
 
• Blood Draw
 
• Echo
 
• Device Interrogation (initial)
 
• Save-to-Media (initial)
 
• Program the sleep function to OFF if subject still has sleep function ON (and program the pacing parameters)
 
• Device Interrogation (final) - this needs to be completed at the end of the visit after programming has been completed
 
• Save-to-Media (final)
 

--	--

	
 
• Adverse Events (report new/assess ongoing AEs), Study Deviations, System Modifications, Device Deficiencies, Crossovers (as they occur)
 
 
10 Week Telephone Call Follow Up Visit:
 
 
• Symptom Assessment
 
• Heart Rate
 
 
12 Week In-Clinic Follow Up Visit (Exit):
 
 
• Medications
 
• Physical Assessment (including weight, heart rate and blood pressure)
 
• NYHA classification
 
• MN Living with Heart Failure Questionnaire
 
• 6 Minute Walk Test
 
• Blood Draw
 
• Echo
 
• Device Interrogation (initial)
 
• Save-to-Media (initial)
 
• Device Interrogation (final) - this needs to be completed at the end of the visit after programming has been completed
 
• Save-to-Media (final)
 
• Adverse Events (report new/assess ongoing AEs), Study Deviations, System Modifications, Device Deficiencies, Crossovers
 
 
Early study exit (prior to 12 week visit):
 
 
• Date of visit
 
• Reason for exit
 
• Adverse Events (report new/assess ongoing AEs), Study Deviations, System Modifications, Device Deficiencies, Crossovers
 
• Complete a Scheduled/Unscheduled Follow Up eCRF, if applicable
 
 
Unscheduled Follow Up:
 
The following are recommended at the discretion of the investigator if deemed necessary:
 
 
• Physical Assessment (including weight, heart rate and blood pressure)
 
• Medications
 
• Echo
 
• Blood draw
 
• Device Interrogation (initial)
 
• Save-to-Media (initial)
 
• Program the Sleep Function to protocol
 

--	---

	
 
• Device Interrogation (final) - this needs to be completed at the end of the visit after programming has been completed Save to Media (final)
 
 
The following are required:
 
 
• Adverse Events (report new/assess ongoing AEs), Study Deviations, System Modifications, Device Deficiencies, Crossovers
 

Safety Assessments	Levels of Troponin and NT-proBNP will be monitored at all in office visits to assess for ischemia and elevated wall stress that may indicate worsening heart failure. All Adverse Events (AEs) that are potentially relevant will be collected which include system-related, programming-related, cardiovascular and serious adverse event information throughout the study duration, starting at the time of signing the Informed Consent Form. All new and/or worsening AE information, including all deaths will be collected throughout the clinical study duration. NT-pro BNP and Troponin will be collected at Baseline and at each subsequent in-office visit and changes will be assessed to ensure that the therapy is not leading to undue cardiac stress or ischemia. Documented pre-existing conditions are not considered an AE unless the nature or severity of the condition has worsened.
Endpoints	A number of measures of therapy safety, tolerability and efficacy will be explored as ancillary endpoints.
Statistics	As a feasibility study, this study is not powered to meet any specific endpoints.

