### 7.2. Rationale

It is expected that up to 50 subjects may be enrolled to ensure approximately 30 subjects will have elevated night pacing programmed ON for the first 4 weeks in order to evaluate whether the therapy is symptomatic. Limitations to the programming of the Sleep Function requires subjects to have a lower

rate of 100bpm programmed between the time they leave the Baseline visit and 5am the next morning when "Bed Time" will set the Sleep Rate at the pre-study lower rate of 60-70bpm. At the 4 week visit, there will be a safety assessment. Measurements of NT-proBNP will be used to assess whether dilation of the heart is signalling worsening heart failure. A Troponin assay will be used to ensure the elevated night pacing therapy isn't leading to ischemia. Subjects will be randomized at 4 weeks to elevated night pacing ON or OFF in order to gather data on the dose-response of the elevated night pacing therapy. Some patients may have sensation of an elevated heart rate from this programming, making blinded randomization difficult to achieve. All subjects will be followed for at least 4 weeks following termination of the elevated night pacing therapy in order to evaluate whether changes in quality of life, 6 minute walk tests and echo measurements persist after the therapy is discontinued. Previous work in animal studies have shown that cessation of elevated pacing rates can reverse the dilation of the LV chamber; this study will monitor the time course of that reversal by serial echo measurements, 6 minute walk tests and activity counts, and quality of life assessments.

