### 14.1.2. Ancillary Safety Endpoint – NT-proBNP, troponin, LVEF

#### NT-proBNP, troponin, LVEF – 4 weeks

##### Hypothesis

For each of the main safety measures (NT-proBNP, troponin and LVEF), comparisons will be done to see if there are changes from baseline after a 4 week period of elevated night pacing.

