##### Analysis Methods

The proportion of subjects who remain in the study up until the 4 week visit without exiting due to intolerable symptoms, increase in NT-proBNP levels, decrease in LVEF or increase in troponin will be calculated along with the lower bound of the one-sided 95% confidence interval.

As the REVAMP study was designed to explore the feasibility of the study therapy, there was no pre-specified threshold for overall safety and tolerability. In order to provide the most conservative estimate of the safety and tolerability, any study exit prior to the 4 week visit will be assumed to be related to intolerable symptoms or safety issue. Also, study

deaths attributed by the investigative site as related or unknown relative to the study therapy prior to the 4 week visit will be counted against the proportion of subjects remaining in the study. A variable active4wk will be set to equal 1 for subjects who remain in the study up until the 4 week visit and will be set to equal 0 otherwise. The proportion of subjects remaining in the study, along with the lower bound of the one-sided 95% confidence interval can be found using code similar to:

```
PROC FREQ DATA=Revamp_Test;
  TABLE active4wk / BINOMIAL(EXACT LEVEL='1') ALPHA=0.1;
RUN;
```

As this study is exploring the feasibility of the study therapy, sensitivity analysis may be performed, exploring various assumptions regarding ambiguous study exits.

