###### Analysis Methods

A paired comparison of the value at the end of the period compared to the value at the start of the period will be calculated. A two-sided paired t-test will be performed testing the hypothesis

$$H_0: \mu = 0$$

$$H_a: \mu \neq 0$$

Where  $\mu$  = difference in measurement from baseline to week 4 visit

SAS code similar to the following will be used to evaluate the 4 week ancillary safety endpoints:

```
PROC TTEST;
  PAIRED ntprobp0*ntprobp4;
RUN;

PROC TTEST;
```

```
PAIRED troponin0*troponin4;  
RUN;  
  
PROC TTEST;  
  PAIRED lvef0*lvef4;  
RUN;
```

By default, subjects that do not have 4 week measurements available will be excluded from the analysis.

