#### Analysis Methods

A paired comparison of the measurement at the 8 week visit compared to the measurement at the 4 week visit period compared to the value at the start of the period will be calculated. A two-sided paired t-test will be performed testing the hypothesis

$$H_0: \mu_{ON} = \mu_{OFF}$$

$$H_a: \mu_{ON} \neq \mu_{OFF}$$

Where  $\mu_{ON}$  = difference in NT-proBNP, troponin or LVEF from week 4 to week 8 for subjects in the ON arm and  $\mu_{OFF}$  = difference in those measurements in subjects in the OFF arm

SAS code similar to the following will be used to evaluate the 8 week ancillary safety endpoints, where the variables in the VAR statement will equal the difference between the 8 week and 4 week measurements:

```
PROC TTEST;
  CLASS trt;
  VAR ntpobnppdiff;
RUN;

PROC TTEST;
  CLASS trt;
  VAR troponindiff;
RUN;

PROC TTEST;
  CLASS trt;
  VAR lvefdiff;
RUN;
```

An ANCOVA model may also be used for all analyses prospectively planned as T-tests, in addition to the T-tests for this and other similar ancillary objectives comparing the 4 and 8 week data by randomized treatment group. ANCOVA models may be implemented using SAS code similar to

```
PROC GLM;
  CLASS trt;
  MODEL ntpobnppdiff= trt ntpobnpp0;
  LSMEANS trt / pdiff cl alpha=0.05;;
RUN;
```

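### The dedicated NT-proBNP, troponin and LVEF analyses are difference tests on group means; they cannot support the aim to ensure no cardiac stress or ischemia, and no planned table counts marker rises

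*Protocol*

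**What the plan says.** **Purpose.** The synopsis (Safety Assessments) has both markers drawn at Baseline and at each office visit, and states that "changes will be assessed to ensure that the therapy is not leading to undue cardiac stress or ischemia". Protocol 7.2 gives troponin the same task: "A Troponin assay will be used to ensure the elevated night pacing therapy", it continues, is not producing ischemia.

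**Analysis.** At week 4, Protocol 14.1.2 says that "comparisons will be done to see if there are changes from baseline after a 4 week period of elevated night pacing". SAP 7.9.2 implements this as a test of zero mean change: "A two-sided paired t-test will be performed testing the hypothesis". Subjects who withdrew from treatment in the first four weeks, for safety or other reasons, are left out. For weeks 4 to 8 the SAP tests whether the "difference in NT-proBNP, troponin or LVEF from week 4 to week 8 for subjects in the ON arm" equals that in the OFF arm. The text calls this test paired, but the code is a two-sample t-test, with an optional ANCOVA.

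**Contrast.** For the exit-based tolerability proportion, SAP 7.9.1 does report a bound: the proportion is given "along with the lower bound of the one-sided 95% confidence interval".

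**Handling of individual subjects.** Protocol 10.19 asks investigators to watch subjects with marker increases for symptoms. Protocol 10.11 covers stopping pacing for abnormal values. Table 9 says pacing will be programmed off if levels worsen. The adverse event definition in Table 10 includes abnormal laboratory findings. The exit endpoint (14.1.1) names marker increases as a reason for exit.

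**The concern.** The stated purpose is to exclude harm, while the analysis looks for a difference. The two answer opposite questions. With about 30 subjects, failure to reject zero change is compatible with a real rise, so it cannot carry the word *ensure*. The test also concerns the group mean, whereas ischemia and decompensation occur in individuals. If a few subjects have large rises and the rest have none, the mean test will usually be non-significant, and no other planned table would show those rises as such. At stake is whether the study report can say anything reliable about marker safety.

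**Working it through.** **1. Inputs.** Up to 30 paced subjects (Protocol 14). Allocation is 2:1, so about 20 ON and 10 OFF if all are randomised. Two-sided alpha 0.05 is assumed for the t-tests: their code sets no level, and 0.05 appears in SAP 7.9.2 only in the ANCOVA line, "LSMEANS trt / pdiff cl alpha=0.05". The documents give no standard deviation (SD), effect size, power or margin for the markers, so there is no plan figure to reproduce. I assume an SD of the individual log change of 0.3 to 0.6.

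**2. Can the other endpoint see a marker rise?**
- The 4-week endpoint counts subjects who stay in the study up to the 4-week visit. The only scheduled post-baseline blood sample in that period is drawn at that visit (Protocol Table 4), so a rise first found in it cannot have caused an earlier exit.
- Under 10.11, a subject whose pacing is stopped for abnormal markers is still followed to week 12. That is not an exit, so the 8-week endpoint counts the subject as remaining.
- 10.11 refers to abnormal values as defined in 10.19, but 10.19 gives numbers only for LVEF.
- 10.19 asks for symptoms to be reported as adverse events. No cut-off says when a symptomless rise is one.

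**3. Three of 30 affected, no noise.** Let 3 subjects rise by the same amount r and 27 not change at all.
- Mean = 3r/30 = 0.100r
- SD = r × √[3 × 27 / (30 × 29)] = 0.305r
- SE = 0.305r / √30 = 0.0557r
- t = 0.100 / 0.0557 = 1.80; the critical value on 29 df is 2.045

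r cancels. However large the common rise, the test is not significant, because the affected subjects inflate the SD together with the mean.

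**4. With noise (simulation, log scale, n = 30, 3 subjects affected).** Share of trials with a significant rise:

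| SD of log change | 2-fold rise | 3-fold rise |
|---|---|---|
| 0.3 | 12% | 16% |
| 0.4 | 10% | 14% |
| 0.6 | 7% | 10% |

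A separate simulation in SD units, with shifts of 2 to 5 SD, gives 4-5% with one subject affected, 7-9% with two, 11-18% with three and 24-57% with five.

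**5. A 20% rise in everyone.** Standardised effect = ln(1.2)/SD = 0.182/SD, that is 0.61, 0.46 and 0.30 at SD 0.3, 0.4 and 0.6. Power by noncentral t:
- Week 4, n = 30, noncentrality effect × √30: 90%, 67%, 36%, so missed 10% to 64% of the time.
- Weeks 4 to 8, a 20% excess in ON, 20 against 10, noncentrality effect / √(1/20 + 1/10): 33%, 21%, 12%, so missed 67% to 88% of the time.

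**6. What estimation would show instead.**
- If the observed mean log change is zero with n = 30, the one-sided 95% upper bound is exp(1.699 × SD / √30). This is a rise of 10%, 13% or 20% at SD 0.3, 0.4 or 0.6.
- Zero subjects with a given rise leaves an exact one-sided upper bound of 1 − 0.05^(1/30) = 9.5% (0 of 20: 13.9%). With 3 of 30 the bound is 23.9%.
- If 10% of subjects truly have such a rise, a count shows at least one with probability 1 − 0.9^30 = 96% (79% if 5%).

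The count therefore shows what the mean test usually misses. The bounds also show that *ensure* is out of reach at this sample size whichever analysis is used.

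**The case against.** The plan is candid about its limits: "As a feasibility study, this study is not powered to meet any specific endpoints". These endpoints are ancillary, the hypothesis is worded neutrally, and low power is not an error in a feasibility study. That stands. The complaint is the mismatch between stated purpose and analysis, not the power.

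*Ensure* can also be read as describing the monitoring of each subject rather than a group test. That is a fair reading of part of the text, and the provisions in 10.11, 10.19 and Tables 9 and 10 are real. They govern care, however, and produce no planned summary of rises.

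A reader might infer four stronger points that the documents do not support:
- *A non-significant result will be reported as safe.* No such rule is written.
- *The decision to proceed rests on these tests.* Protocol 14 and SAP 6 name the 4-week exit endpoint instead, and SAP 7.9.1 counts any earlier exit against the therapy.
- *Harm in a few subjects goes unnoticed.* That describes the mean test, not the whole plan.
- *A moderate rise in everyone would usually be missed.* At week 4 a 20% rise is detected more often than not at two of the three assumed SDs.

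A count has weaknesses too. By chance alone, 1 − Φ(ln 2 / SD) of unaffected subjects would double: 1.0%, 4.2% or 12.4%, that is 0.3, 1.2 or 3.7 of 30. The first four weeks have no control arm. The NT-proBNP figure of 300 pg/ml in Protocol 5.1 is quoted there as a threshold for acute heart failure. Neither doubling nor that figure should stand as the sole criterion.

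**Conclusion.** The point holds as a mismatch between purpose and analysis. The dedicated analyses of the principal safety measures are two-sided difference tests on means among four-week completers, with no bound, no margin and no subject-level summary. A non-significant result cannot support *ensure*. With 3 of 30 subjects affected, a significant rise appears in about 7% to 18% of trials. That range rests on an assumed log SD of 0.3 to 0.6 with 2- or 3-fold rises, or shifts of 2 to 5 SD, and on alpha 0.05. The noise-free result in step 3 needs no SD assumption. The exit endpoint does not fill the gap, because of when the sample is drawn and because stopping pacing is not an exit. The finding concerns what the report can claim. It does not show that subjects are unprotected or that the decision rule is wrong. It is worth correcting but does not threaten the study.

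**What to change.** In SAP 7.9.2, make estimation the stated safety analysis.

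- **Bounds.** Report the mean change (log scale for NT-proBNP and troponin) with one-sided 95% upper bounds for the markers and a lower bound for LVEF. Do this from Baseline to week 4 in all paced subjects with a sample, including those who stopped pacing or left early, and from Baseline to week 8 by randomised arm. State how many subjects have no sample, since Table 4 schedules no blood draw or echo at early exit.
- **Subjects.** Show individual changes and the number of subjects in fold-change categories fixed before unblinding, by arm after week 4, with exact one-sided 95% upper bounds. Label this descriptive, because the first four weeks are uncontrolled and some rises occur by chance. Also count subjects whose pacing was stopped for marker changes.
- **Wording.** State that a non-significant t-test is not read as absence of harm. In the synopsis and Protocol 7.2, replace *ensure* with *estimate* where it describes the analysis.
- **Consistency.** Protocol 10.11 (points to a definition), 10.19 (defines no abnormal marker value and leaves action to discretion) and Table 9 (pacing will be programmed off) must be reconciled. No clinical cut-off or rule is proposed here; the categories above serve the analysis only.

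The cost is SAP and Protocol wording and one extra table from data already collected. The safety statement becomes less favourable: even no affected subjects in 30 would be reported with an upper bound of 9.5%.
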